3.1.3. Adverse Events

The time period for actively eliciting and collecting AEs (“active collection period”) for each participant begins from the time the participant provides informed consent, which is obtained before the participant’s participation in the study (ie, before undergoing any study-related procedure and/or receiving study intervention), through and including Visit 102 in Substudy A (approximately 4 weeks after vaccination).

Additionally, MAEs, NDCMCs, and SAEs will be collected from the time the participant provides informed consent to Visit 103 in Substudy A (approximately 6 months after vaccination). In addition, AEs occurring up to 48 hours after blood draws must be recorded on the CRF.

Standard algorithms for handling missing AE dates and missing AE severity will be applied as described in the Pfizer data standard rules.

The following derivations will be included for each participant:

- Any AE reported.
- Any related AE reported.
- Any immediate AE (assess acute reactions for at least 30 minutes after study intervention administration).
- Any SAE.
- Any MAE (an MAE is defined as a nonserious AE that results in an evaluation at a medical facility).
- Any NDCMC (an NDCMC is defined as a disease or medical condition, not previously identified, that is expected to be persistent or otherwise long-lasting in its effects [eg, asthma]).
- Any severe AE.
- Any life-threatening AE.
- Any AE leading to study withdrawal.
- Any AE leading to death.
- Any AESI.
 - Confirmed diagnosis of influenza (clinical signs/symptoms and positive laboratory testing) after Day 1 through 6 months after vaccination.
 - Confirmed diagnosis of myocarditis or pericarditis occurring within 28 days after vaccination.

3.2. Secondary Endpoint(s)

- HAI titers for the 2023-2024 northern hemisphere seasonal strains recommended by WHO for CCI influenza vaccines at baseline and 4 weeks after vaccination.

090177e1a0eba359Approved\Approved On: 13-Jun-2024 14:08 (GMT)

3.3. Other Safety Endpoint(s)

3.3.1. Physical Examinations, Vital Signs, and Medical History

A physical examination may be performed at baseline (Visit 101 in Substudy A) prior to vaccination, if clinically indicated. Physical examination findings collected during the study will be considered source record and will not be required to be reported, unless otherwise noted. Any untoward physical examination findings that are identified during the active collection period and meet the definition of an AE or SAE will be recorded in the CRF.

The participant's oral temperature will be measured prior to vaccination in Substudy A. Any untoward vital sign findings that are identified during the active collection period and meet the definition of an AE or SAE will be recorded in the CRF.

Medical history will be categorized according to MedDRA.

CCI

3.5. Baseline Variables

Measurements or samples collected prior to vaccination are considered the baseline data for the assessments. In this study, Day 1 is the baseline visit; the data from screening visit may be used as baseline only if the data on Day 1 are missing.

3.5.1. Demographics

The demographic variables are age at the first vaccination (in years), sex (male or female), race (Black/African American, American Indian or Alaska Native, Asian, Native Hawaiian or other Pacific Islander, White, not reported), and ethnicity (Hispanic/Latino/of Spanish origin, non-Hispanic/non-Latino/non-of Spanish origin, not reported), and racial designation (Japanese, other). In cases where more than 1 category is selected for race, the participant would be counted under the category “multiracial” for analysis.

3.5.2. E-Diary Completion

An e-diary will be considered transmitted if any data for the 3 local reactions (redness, swelling, and pain at the injection site) and 8 systemic events (fever, vomiting, diarrhea, headache, fatigue, chills, new or worsened muscle pain, and new or worsened joint pain) are present on any day. If all data are missing for all items on the e-diary for all 7 days after vaccination, then the e-diary will be considered not transmitted.

An e-diary will be considered completed if all expected data for all 7 days are available (ie, not missing). Otherwise, the e-diary will be considered incomplete. For any given day, an e-diary will be considered complete if all expected data are available.

Note: Data entered as part of the 72-hour recall period will be counted for the e-diary completion/transmission.

The data from the Participant Reported Reactogenicity CRF page will not be included in the e-diary completion/transmission summary.

For transmitted e-diaries, the following variables will be defined: “Day 1,” “Day 2,” “Day 3,” “Day 4,” “Day 5,” “Day 6,” and “Day 7.”

For completed e-diaries, the following variables will be defined: “Day 1,” “Day 2,” “Day 3,” “Day 4,” “Day 5,” “Day 6,” “Day 7,” and “Day 1-Day 7.”

“Day 1-Day 7” is the variable for participants who completed e-diaries on all 7 days.

For e-diaries that are incomplete, an indicator variable for the percentage of days without data will be derived as follows:

- = 1, if data have been transmitted and are complete for 7 days (100%)
- = 2, if data have been transmitted and are complete for 6 days ($\geq 75\%$ to $< 100\%$)
- = 3, if data have been transmitted and are complete for 4 or 5 days ($\geq 50\%$ to $< 75\%$)
- = 4, if data have been transmitted and are complete for 2 or 3 days ($\geq 25\%$ to $< 50\%$)
- = 5, if data have been transmitted and are complete for 0 or 1 day ($< 25\%$)

3.5.3. Prior/Concomitant Vaccines and Concomitant Medications

The following concomitant medications and vaccinations will be recorded in the CRF:

- Any vaccinations received from 28 days prior to study enrollment until the last visit (Visit 103).
- Last dose of licensed influenza vaccine, if received.

- Prior receipt of any mRNA vaccine (eg, mRNA-based COVID-19 vaccine).
- Prohibited medications listed in [Section 10.11.6.9.1 of the protocol](#), if taken, will be recorded and include start and stop dates, name of the medication, dose, unit, route, and frequency.

Nonstudy vaccines and concomitant medications will be coded using the WHODD.

4. ANALYSIS SETS (POPULATIONS FOR ANALYSIS)

Data for all participants will be assessed to determine if participants meet the criteria for inclusion in each analysis population prior to unblinding and releasing the database, and classifications will be documented per standard operating procedures.

Population	Description
Screened	All participants who sign the ICD.
Randomized	All participants who are assigned a randomization number in the IRT system.
CCI	
Safety	All participants who receive the study intervention.

090177e1a0eba359\Approved\Approved On: 13-Jun-2024 14:08 (GMT)

Important protocol deviations will be determined by clinical review. An important protocol deviation is a protocol deviation that, in the opinion of the sponsor's clinician, would materially affect assessment of immunogenicity, eg, participant receipt of a prohibited vaccine or medication/treatment that might affect immune response or a medication error with a suspected decrease in potency of the vaccine. The sponsor's clinician will identify those participants with protocol deviations that result in exclusion from analysis populations before any unblinded analysis is carried out.

The APE field will be included in the PIPD list from the CORD system and is used to help identify protocol deviations that may exclude participants from a particular population. For each reporting event, the most current endorsed version of the PIPD list must be used to generate the protocol deviation data set for analysis and reporting.

The APE flags for this study are as follows:

- YES-POP1 (participants excluded from the safety population)
- YES-POP2 (participants excluded from the evaluable immunogenicity population)
- YES-POP3 (participants identified as multiple enrollers)

Participants enrolling at multiple sites (multiple enroller): Any participant enrolling at more than 1 site in the study will be removed from the evaluable, mITT, and safety populations. These participants will be followed for safety and reported separately from the other participants.

Vaccinated but not randomized: These participants will be included in the safety population for safety analysis and will be reported under the vaccine group based on the vaccine received but will be excluded from the evaluable immunogenicity analyses or mITT immunogenicity analyses.

Randomized but not vaccinated: These participants will be included in the randomized population and excluded from any safety analyses and evaluable immunogenicity or mITT immunogenicity analyses.

Randomized but received incorrect vaccine: These participants will be included in the mITT populations for immunogenicity analyses if data are available and will be reported under the vaccine group based on the randomized vaccine. These participants will also be included in the safety population for safety analysis and will be reported under the vaccine group based on the vaccine received.

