#### **9.4. Interim Analyses**

There are no formal interim analyses planned for any of the substudies. As each substudy is open-label to the sponsor, the sponsor will conduct unblinded reviews of the data during the course of the study for the purpose of safety assessment, dose selection, and/or supporting clinical development.

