#### **10.11.6.4.3. Blinding of the Sponsor**

To facilitate rapid review of data in real time, sponsor staff will be unblinded to study intervention allocation for the participants throughout Substudy A.

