#### 10.11.9.5. Sample Size Determination

Since Substudy A is descriptive in nature, the planned sample size for the study is not based on any statistical hypothesis testing.

Approximately 90 participants will be enrolled in each vaccine group; therefore, a total of approximately up to 450 participants may be enrolled into this substudy.

For safety outcomes in the study, Table 6 shows the probability of observing at least 1 AE for a given true event rate of a particular AE with 90 participants in each vaccine group.

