5. GENERAL METHODOLOGY AND CONVENTIONS

5.1. Hypotheses and Decision Rules

The study is descriptive in nature, no formal statistical hypothesis testing will be performed. No decision rules will be applied.

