5.2. General Methods

CI for all endpoints in the statistical analysis will be presented as 2-sided at the 95% level unless specified otherwise.

The safety analyses are based on the safety population. Participants will be summarized by vaccine group according to the study interventions they actually received. Completely missing reactogenicity e-diary data will not be imputed; missing AE dates will be handled according to the Pfizer safety rules.

For the immunogenicity endpoints, the main analysis will be based on the evaluable immunogenicity population. Antibody titers below the LLOQ, denoted as BLQ, will be set to $0.5 \times \text{LLOQ}$ for GMT analysis. No other missing assay data will be imputed in the analyses. All immunogenicity analyses will be performed after the imputation of the antibody titers that are below the LLOQ.

An additional analysis may be performed based on the mITT immunogenicity populations if there is a large enough difference ($>10\%$) in sample size between the mITT immunogenicity population and the evaluable immunogenicity population. Participants will be summarized according to the vaccine group to which they were randomized. Missing serology data will not be imputed.

No formal multiplicity adjustments will be applied for the analyses in multiple endpoints or for multiple looks of the same endpoint due to the descriptive nature of this substudy.

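### The SAPs describe analysis-population exclusions as decided before unblinding, but the sponsor is unblinded throughout, and nothing ensures that the discretionary exclusions are locked before HAI results are seen

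*SAP*

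**What the plan says.** Section 4 of the SAPs for Substudies A, B and C makes two statements about timing. Membership of each analysis population is to be assessed "prior to unblinding and releasing the database". And the sponsor's "clinician will identify those participants with protocol deviations" "that result in exclusion from analysis populations before any unblinded analysis is carried out". An important deviation is one that this clinician judges would materially affect the assessment of immunogenicity. The deviation data set is rebuilt at each reporting event from the latest endorsed list.

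The protocol describes a sponsor that is not blind. For Substudy A, section 10.11.6.4.3 states that "sponsor staff will be unblinded to study intervention allocation for the participants throughout Substudy A"; sections 10.12.6.4.3 and 10.13.6.4.3 say the same for B and C. Section 9.4 adds that "the sponsor will conduct unblinded reviews of the data during the course of the study", with dose selection among the stated purposes, and section 7.1 of each SAP repeats this. The synopsis also allows informal analyses.

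For HAI in Substudies A and B, the main analysis uses the evaluable immunogenicity population. On the alternative population, SAP section 5.2 says: "An additional analysis may be performed based on the mITT immunogenicity populations if there is a large enough difference", with more than 10% given as large enough. SAP section 6.2.1.2 is equally permissive and gives no threshold. Protocol section 9.3.1 gives no number. The corresponding text in section 5.2 of the Substudy C SAP is redacted.

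**The concern.** Classifying participants before unblinding protects an analysis because whoever decides on exclusions cannot know which group, or which result, a decision favours. Here the decision rests partly on opinion and is made within a party that already knows allocation. There is no later unblinding event for it to precede. A reader of the study report would credit the immunogenicity results with a protection that the design does not provide.

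This matters even in a descriptive study. Protocol section 10.11.2.1 says Substudy A will inform the choice of reformulation, section 10.12.2.1 says the same for B, and SAP section 6.2.1.1 compares each tIRV with each control by GMR. No confidence interval reflects a selective exclusion, and the analysis that would reveal one need not be run.

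**Working it through.** **The plan's own figures.** The plan gives no calculation on this point. SAP section 5.1 says that "no formal statistical hypothesis testing will be performed", so no alpha, power or margin is involved. The only sample-size figures for Substudy A, in protocol Table 6, do reproduce (for example 1 − 0.99^90 = 59.5% at a 1% event rate), but they do not bear on exclusions.

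**Side by side.**
- Who decides: the sponsor's clinician (SAP section 4).
- What the sponsor knows: allocation, throughout (protocol 10.11.6.4.3, 10.12.6.4.3, 10.13.6.4.3). The stopping-rule sections confirm that the study team can see individual allocation.
- Whether the deciding clinician is kept apart from allocation or titres: no visible text says so.
- Whether the list is locked relative to HAI results: not stated. SAP section 5.2 anticipates several looks at one endpoint, and the list is renewed at each reporting event.

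**What the 10% condition does in A and B.** Protocol section 10.11.9.5: "Approximately 90 participants will be enrolled in each vaccine group"; Substudy B plans the same number.
- With 90 in the mITT group as denominator, 9/90 = 10.0%, which is not more than 10%.
- With the evaluable group as denominator, 8/82 = 9.8% is below the condition and 9/81 = 11.1% is above it.
- Pooled over 5 × 90 = 450, 45 exclusions do not exceed 10%, however they are distributed among groups.
- The SAPs do not say which denominator applies, and above 10% the analysis is still only permitted.

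**Illustrative size for a GMT.** Assumptions, none given in the documents: those excluded average 0.5 to 0.8 log10 below those kept; log10 SD 0.55; 90 in the mITT group; 9 excluded, all in the same direction.
- Shift in mean log10 titre = (9/90) × gap = 0.10 × 0.5 to 0.10 × 0.8 = 0.05 to 0.08.
- GMT factor = 10^0.05 to 10^0.08 = 1.12 to 1.20.
- 95% sampling factor for a GMR = 10^(1.96 × 0.55 × √(2/90)) = 10^0.161 = 1.45.
- On the log scale the shift is 0.05/0.161 to 0.08/0.161, or about 0.31 to 0.50 of the half-width.

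**Outer bound for seroconversion.** Assume 45 of 90 seroconvert (50%; Clopper-Pearson 95% CI 39.3% to 60.7%). Removing 9 non-responders gives 45/81 = 55.6%; removing 9 responders gives 36/81 = 44.4%. The span is 9/81 = 11.1 percentage points.

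These figures show what the text would permit. They do not predict what will happen.

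**The case against.** The strongest reply is that the sentence in SAP section 4 also sets an order of work, with exclusions first and by-group analysis afterwards, and that this order can be kept by an unblinded sponsor. That stands. A reader might infer that no safeguard exists at all, or that exclusions will be made with titres in view. The documents support neither. What is lost is masking of allocation. The order remains possible but is not secured, and renewing the deviation list may be ordinary version control as deviations accrue.

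The discretion is also narrower than it first appears. SAP section 4 gives concrete examples: a prohibited vaccine or treatment that might affect the response, or an error that may have reduced potency. Section 2.2.2 of the A and B SAPs lists rule-based grounds: eligibility, vaccine not as randomized, and blood drawn before day 26 or after day 35. Laboratory analysts work on coded samples (protocol 8.2.2), site evaluators are blinded, and exclusions are tabulated by group with reasons (SAP 6.6.2.1). All of this stands and limits the exposure. None of it masks the discretionary decision, and a table of counts does not show the effect on a GMT.

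A reader might also take 10% as the most that can be excluded unchecked. It is neither a ceiling nor a trigger: an mITT summary below 10% is not barred, and one above 10% is not required. Nor can the mITT point be carried to Substudy C, where the text is redacted and there is no secondary endpoint (SAP C, 3.2 and 6.2). The evaluable and mITT definitions are redacted too, so the share of exclusions that turns on opinion cannot be judged.

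Finally, the illustrated shift lies within the sampling factor and rests on assumed inputs. That is correct. It supports treating this as a correctable weakness and not as a threat to the study.

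**Conclusion.** The point holds in a limited form. In all three SAPs the statements about unblinding conflict with the protocol's sponsor-unblinded design, and no visible text restores masking for the person who decides. Nothing secures that opinion-based exclusions are locked before HAI results are seen.

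The consequence falls on the secondary, descriptive immunogenicity results in A and B, and only through discretionary deviations. The primary safety analysis uses the safety population, defined as everyone vaccinated, and does not depend on the evaluable population. In A and B the mITT comparison is optional at every level of exclusion, and the denominator of the 10% is undefined.

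The illustrated size, a GMT factor of 1.12 to 1.20 against a GMR sampling factor of 1.45, depends entirely on the assumed titre gap, the assumed SD, an mITT group of 90 and exclusions all in one direction. The wording conflict depends on none of these.

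**What to change.** - **Section 4 of all three SAPs:** replace both statements about unblinding with one saying that the sponsor is unblinded to allocation, and that the exclusion list for each reporting event is frozen and dated before that event's immunogenicity results are transferred from the laboratory. List any later change with its reason. This does not restore masking of allocation. It makes the decisions independent of the titres, which is the protection still available in this design.
- **SAPs A and B, sections 5.2 and 6.2.1.2:** show the mITT HAI results (GMT, GMFR, GMR and seroconversion) beside the evaluable results as a matter of course, and delete the 10% condition. The question of its denominator then disappears.

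The cost is SAP wording, one dated list per transfer and one repeat of existing tables. No data collection changes.

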5. GENERAL METHODOLOGY AND CONVENTIONS

5.1. Hypotheses and Decision Rules

The study is descriptive in nature, no formal statistical hypothesis testing will be performed. No decision rules will be applied.

5.2. General Methods

CI for all endpoints in the statistical analysis will be presented as 2-sided at the 95% level unless specified otherwise.

The safety analyses are based on the safety population. Participants will be summarized by vaccine group according to the study interventions they actually received. Completely missing reactogenicity e-diary data will not be imputed; missing AE dates will be handled according to the Pfizer safety rules.

For the immunogenicity endpoints, the main analysis will be based on the evaluable immunogenicity population. Antibody titers below the LLOQ, denoted as BLQ, will be set to $0.5 \times \text{LLOQ}$ for GMT analysis. No other missing assay data will be imputed in the analyses. All immunogenicity analyses will be performed after the imputation of the antibody titers that are below the LLOQ.

An additional analysis may be performed based on the mITT immunogenicity populations if there is a large enough difference ($>10\%$) in sample size between the mITT immunogenicity population and the evaluable immunogenicity population. Participants will be summarized according to the vaccine group to which they were randomized. Missing serology data will not be imputed.

No formal multiplicity adjustments will be applied for the analyses in multiple endpoints or for multiple looks of the same endpoint due to the descriptive nature of this substudy.

5.2.1. Analyses for Binary Endpoints

Descriptive statistics for binary variables (eg, proportions) are the percentage (%), the numerator (n) and the denominator (N) used in the percentage calculation, and the 95% CIs where applicable.

The exact 95% CI for binary endpoints for each group will be computed using the F distribution (Clopper-Pearson)¹ and implemented in SAS PROC FREQ.

5.2.2. Analyses for Continuous Endpoints

Unless otherwise stated, descriptive statistics for continuous variables are n, mean, median, standard deviation, minimum, and maximum.

5.2.2.1. Geometric Mean Titers

The GMTs will be calculated as the mean of the assay results after making the logarithm transformation and then exponentiating the mean to express results on the original scale. Two-sided 95% CIs will be obtained by taking log transforms of assay results, calculating the 95% CI based on the Student t distribution, and then exponentiating the confidence limits.

5.2.2.2. Geometric Mean Fold Rises

GMFRs are defined as the geometric mean of the fold rise in the assay results from before to a specified time point after vaccination. GMFRs are limited to participants with nonmissing values at both time points.

GMFRs will be calculated as the mean difference of logarithmically transformed assay results (later time point minus earlier time point) and exponentiating the mean difference. The associated 2-sided 95% CIs will be obtained by constructing CIs using the Student t distribution for the mean difference on the logarithm scale and exponentiating the confidence limits.

5.2.2.3. Geometric Mean Ratios

The GMR will be calculated as the mean of the difference of logarithmically transformed assay results and exponentiating the mean. Two-sided CIs will be obtained by calculating CIs using the Student t distribution for the mean difference of the logarithmically transformed assay results and exponentiating the confidence limits.

